### 3. STUDY DESIGN

[figure not shown]
#### 3.1. GENERAL DESCRIPTION

D8111C00010 is a Phase IV, open-label, non-randomized, multi-cohort, multicenter study of the immunogenicity and safety of AZD1222 for the prevention of COVID-19 in previously unvaccinated immunocompromised adults  $\geq 18$  years. Immunocompromised participants will receive primary vaccination with 3 IM doses of AZD1222 separated by 4 weeks and will continue to be followed to the end of the study. Immunocompetent participants will receive a primary vaccination series with 2 IM doses of AZD1222 separated by 4 weeks followed by a third dose booster 6 months after dose 1 and will continue to be followed to the end of the study.

The study includes adults  $\geq 18$  years with stable immunocompromising conditions or on stable doses of immunocompromising therapeutics, enrolled in 5 disease cohorts of approximately 60 participants each. A sixth cohort will contain approximately 60 immunocompetent participants. Participants will be allocated to the immunocompromised according to the underlying aetiology of their immunocompromised status.

**Table B: Study Design for Immunocompromised Participants**

**Table C: Study Design for Immunocompetent Participants**

### 3.2. SCHEDULE OF EVENTS

Schedule of events can be found in Section 1.3 of the protocol.

### 3.3. CHANGES TO ANALYSES FROM PROTOCOL

There are no changes to the analyses planned in the protocol.

## 4. PLANNED ANALYSES

### 4.1. DATA MONITORING COMMITTEE

There will be no Data Monitoring Committee (DMC) for this study.

### 4.2. PRIMARY ANALYSIS

A primary analysis will occur when all participants within a cohort have completed visit 8 (i.e., 28 days after the second dose). The data cut-off date will be the date the last participant reaches the trigger for the primary analysis and the corresponding data will be coded and cleaned up to the data cut-off date. Additional primary analyses and data cut-offs may occur after all participants within a given cohort have completed visit 8 depending on participant recruitment.

### **4.3. SECONDARY ANALYSIS**

A secondary analyses of a third dose (primary series) will occur when all participants within an immunocompromised cohort have completed visit 10 (i.e., 28 days after the third dose). The data cut-off date will be the date the last participant reaches the trigger for the secondary analysis and the corresponding data will be coded and cleaned up to the data cut-off date. Additional secondary analyses and data cut-offs may occur after all participants within a given cohort have completed visit 10 depending on participant recruitment.

### **4.4. FINAL ANALYSIS**

All final, planned analyses identified in this SAP will be performed by IQVIA Biostatistics following Sponsor authorization of this SAP, Sponsor authorization of the analysis sets, and database lock (DBL). All participants in the study will be assessed for immunogenicity and safety to the end of the study. The final DBL will occur when all participants have completed the study.

## **5. ANALYSIS SETS**

### **5.1. ALL PARTICIPANTS ANALYSIS SET**

The all participants analysis (PAS) set will contain all participants screened for the study. All participants analysis set is to be used for reporting disposition and screening failures.

All participants screened are those who provide informed consent.

### **5.2. FULL ANALYSIS SET**

The full analysis set (FAS) will contain all enrolled participants, i.e., those participants who meet screening eligibility criteria. Participants who withdraw consent to participate in the study will be included up to the date of their study withdrawal.

### 5.3. SAFETY ANALYSIS SET

The safety analysis set (SAF) consists of all participants who have received at least one dose of study intervention.

A participant who has on one or several occasions received active study intervention is classified as active for all summaries, including summaries by dose.

### 5.4. IMMUNOGENICITY ANALYSIS SET

The immunogenicity analysis (IAS) set will include all participants in the safety analysis set who have at least one baseline and post-baseline record in immunogenicity data and no protocol deviations judged to have the potential to interfere with the generation or interpretation of an immune response. Details of exclusionary protocol deviations will be defined in a separate PD plan (See [Section 9.2](#)). Protocol deviations will be reviewed by the study team before database lock to determine exclusion from the immunogenicity analysis set.

## 6. GENERAL CONSIDERATIONS

### 6.1. REFERENCE START DATE AND STUDY DAY

Study Day will be calculated from the reference start date and will be used to show start/stop day of assessments and events. Reference start date is defined as the day of the first dose of study intervention i.e., Day 1.

Study Day will be computed as follows:

- Study Day = (Date of event – Date of first dose of study intervention) + 1 if the date of the event is on or after the date of the first dose of study intervention.
- Study Day = (Date of event – Date of first dose of study intervention) if the date of the event is prior to the date of the first dose of study intervention.

In addition, day relative to vaccination will be derived for each vaccination dose. For example, day relative to the first dose will be equal to the Study Day. Day relative to the second dose will start with a value of 1 on the day of the second dose.

In the situation where the event date is partial or missing, Study Day and any corresponding durations will appear

partial or missing in the listings.

## 6.2. BASELINE

Unless otherwise specified, baseline is defined as the last non-missing measurement taken prior to the first dose of study intervention (including unscheduled assessments). In the case where the last non-missing measurement and the date and time of the first dose of study intervention coincide, that measurement will be considered pre-baseline, but adverse events (AEs) and medications commencing on the date of the first dose of study intervention will be considered post-baseline.

## 6.3. UNSCHEDULED VISITS, RETESTS, AND EARLY TERMINATION DATA

For by-visit summaries, data recorded at the nominal visit will be presented. That is, unscheduled, retest (same visit number assigned), and early termination measurements will not be included in by-visit summaries but might contribute to the baseline timepoint and/or maximum value, where required (e.g. shift table).

Listings will include scheduled, unscheduled, retest and early discontinuation data.

## 6.4. WINDOWING CONVENTIONS

A windowing convention will be used to determine the analysis value for a given study visit for immunogenicity . The window definitions as following will be used:

1. A window of +/- 7 days from the target day is applied to the V1+14, V1+28, V5+14, V5+28 and V8+28 visits for the immunocompromised participants and to the V1+14, V1+28, V5+14, V5+28 and V9+28 visits for the immunocompetent participants.
2. A window of +/- 30 days from the target day is applied to the V1+182 and V1+364 visits for the immunocompromised participants and to the V1+182 and V1+364 visits for the immunocompetent participants.

One or more results for a particular variable may be obtained in the same visit window. In such an event, the result with the date closest to the expected visit date will be used in the analysis. In the event that two observations are equidistant from the expected visit date, the later observation will be used in the analysis.

**Table D:** Analysis windows for Immunogenicity by Visit (Immunocompromised participants)

Dosing Period	Visit	Day Relative to Dose within the Dosing Period (a)	Visit Window (Study Day) Relative to the Dosing Period
Relative to Dose 1	Baseline (V1)	≤ 1	≤ 1
	V3	15	8 – 21
	V5	29	22 – 35
Relative to Dose 2	V7	15	8 – 21
	V8	29	22 – 35
Relative to Dose 3	V10	29	22 – 35
Relative to Dose 1	V11	183	153 - 212
	V12	365	335 - 394

(a) For each dosing period, the administration of the study intervention is designated as Study Day 1. For analyses within a period, the study day value is incremented by 1 for each date following the vaccine administration. Dates prior to the vaccine administration are decremented by 1, with the date preceding the vaccine administration designated as Study Day -1 (there is no Study Day 0).

**Table E:** Analysis windows for Immunogenicity by Visit (Immunocompetent Participants)

Dosing Period	Visit	Day Relative to Dose within the Dosing Period (a)	Visit Window (Study Day) Relative to the Dosing Period
Relative to Dose 1	Baseline (V1)	≤ 1	≤ 1
	V3	15	8 – 21
	V5	29	22 – 35
Relative to Dose 2	V7	15	8 – 21
	V8	29	22 – 35
Relative to Dose 1	V9	183	153 - 212
Relative to Dose 3	V10	29	22 – 35
Relative to Dose 1	V11	365	335 - 394

(a) For each dosing period, the administration of the study intervention is designated as Study Day 1. For analyses within a period, the study day value is incremented by 1 for each date following the vaccine administration. Dates prior to the vaccine administration are decremented by 1, with the date preceding the vaccine administration designated as Study Day -1 (there is no Study Day 0).

Beside immunogenicity analyses, no visit windowing will be performed for analysis of other variables in this study.

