**Table A: List of Estimands**

Estimand	Attributes				
	Population	Treatment Condition of Interest	Variable/Endpoint	Intercurrent event handling strategy	Population-level summary measure
The immunogenicity of a 2-dose primary vaccination with AZD1222 with a 4-week dosing interval in SARS-CoV-2 naïve immunocompromised adults and immunocompetent adults $\geq 18$ years.	SARS-CoV-2 naïve immunocompromised adults and immunocompetent adults $\geq 18$ years, who don't have exclusionary important protocol deviations (IPDs) and received at least one IM dose of AZD1222.	2 IM doses of AZD1222 with a 4-week dosing interval	a) SARS-CoV-2 specific GMTs in SARS-CoV-2 S and Neutralizing antibodies  b) A binary response, whereby participants who have a post-treatment seroresponse ( $\geq 4$ -fold rise in titres from day of baseline value to 28 days post each dose) as measured by the S and Neutralizing antibodies	For participants who withdraw from the study, or who use restricted medications judged to have the potential to interfere with the generation or interpretation of an immune response, absence of data following these participants' withdrawal or subsequent data following the IPDs will be treated as missing.  Participants who (1) did not receive their second dose of AZD1222 or (2) tested positive	a) GMTs 28 days post each dose in SARS-CoV-2 S and Neutralizing antibodies  b) Number and percentage of participants achieving a seroresponse ( $\geq 4$ -fold rise in titres from day of baseline value to 28 days post each dose) as measured by the S and Neutralizing antibodies

				for SARS-CoV-2 infection (RT-PCR) will be censored at day 29/ the date of the positive test, whichever is earliest.	

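### Section 6.4 assigns immunogenicity samples by closest date without ending the V5 and immunocompetent V9 windows at the dose given at that visit, and its ± text disagrees with Tables D and E by one day

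*SAP*

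**What the plan says.** Section 6.4 applies windowing to immunogenicity only. It expects that "One or more results for a particular variable may be obtained in the same visit window". The choice is then made on date: "In such an event, the result with the date closest to the expected visit date will be used in the analysis". For ties, "In the event that two observations are equidistant from the expected visit date, the later observation will be used in the analysis".

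The text states the widths as "A window of +/- 7 days from the target day is applied to the V1+14, V1+28, V5+14, V5+28 and V8+28 visits" for the immunocompromised cohorts (with V9+28 in place of V8+28 for the immunocompetent) and "A window of +/- 30 days from the target day is applied to the V1+182 and V1+364 visits". Tables D and E then list the limits by day. V5 is counted from dose 1, with target Day 29 and window 22-35. Immunocompetent V9 is also counted from dose 1, with target Day 183 and window 153-212. Dose 2 is given at V5, because V5+14 is Day 15 of dose 2. In the immunocompetent cohort dose 3 is given at V9, because V9+28 is Day 29 of dose 3.

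Section 6.3 gives a general rule: "For by-visit summaries, data recorded at the nominal visit will be presented". It explains this by saying that "unscheduled, retest (same visit number assigned), and early termination measurements will not be included in by-visit summaries". Neither section refers to the other.

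**The concern.** V5 and immunocompetent V9 are both visits at which a dose is given, so their samples are meant to show the response before that dose. Their windows nevertheless continue after it, by 6 days for V5 (35 − 29) and 29 days for V9 (212 − 183) when dosing is on target. Nothing in Section 6.4 requires the chosen sample to precede the dose.

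Other parts of the SAP do not close the gap. The pre-dose rule in Section 6.2 concerns only the first dose. The censoring in Section 16 is triggered by a positive PCR, a non-study COVID-19 vaccine or an exclusionary restricted medication, not by a study dose.

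A 28-day post-booster titre could therefore be reported as the six-month V9 value, or a post-dose-2 titre as the 28-days-post-dose-1 value. If the next dose raises titres, the error is upward. The same V10 sample would also qualify for its own window, and Section 6.4 does not bar using it twice.

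**Working it through.** **Inputs** (Section 6.4, Tables D and E)
- V5: target 29, window 22-35. V7: relative Day 15 of dose 2, window 8-21.
- Immunocompetent V9: target 183, window 153-212. V10: relative Day 29 of dose 3, window 22-35.
- Assumption: the V5 or V9 sample is drawn on the dosing day, before the dose.

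**Step 1. The plan's own limits.** Target plus half-width, against the tables:

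| Target | ± text | Upper limit, text | Upper limit, table |
|---|---|---|---|
| 15 | 7 | 22 | 21 |
| 29 | 7 | 36 | 35 |
| 183 | 30 | 213 | 212 |
| 365 | 30 | 395 | 394 |

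The lower limits agree (8, 22, 153, 335). Every upper limit differs by one day. Under the text, Day 22 lies in both V3 (22 − 15 = 7) and V5 (29 − 22 = 7) and, counted from dose 2, in both V7 and V8.

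**Step 2. V9, table limits.** Dose 3 is on Day d, the V9 sample is on d, and V10 is on d + r − 1, with r = 29 on target.
- V10 lies in the V9 window if d + 28 ≤ 212, so d ≤ 184. For d = 153-184 (32 of the 60 window days) it fills a missing V9. With dose 3 on Day 183, V10 is on Day 211.
- V10 displaces an existing V9 sample if |d + 28 − 183| ≤ |d − 183|. For d ≥ 155 this is d − 155 ≤ 183 − d, so d ≤ 169; Days 153 and 154 also satisfy it. The range is 153-169 (17 of 60 days).
- At d = 160 the distances are 23 (V9) and 5 (V10). At d = 169 they are 14 and 14, and the later sample is used. At d = 170 they are 13 and 15, and V9 is kept.
- With V10 seven days early (r = 22) the range extends to Day 172. With V10 six days late (r = 35) it ends at Day 166.

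**Step 3. V5, table limits.** Dose 2 is on Day d, the V5 sample is on d, and V7 is on d + r − 1. Displacement needs d + r − 1 ≤ 35 and d + r − 30 ≤ 29 − d, so r ≤ 36 − d and r ≤ 59 − 2d, with r at least 8.
- d = 22: r = 8-14
- d = 23: r = 8-13
- d = 24: r = 8-11
- d = 25: r = 8-9
- d = 26: r ≤ 7, so none

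The target is r = 15, so every one of these needs an early V7. A missing V5 can be filled by the earliest V7 for dose 2 up to Day 28 (28 + 7 = 35).

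**Step 4. Effect of the one-day mismatch.** Under the ± text, an on-target V10 fills a missing V9 up to d = 185. With dose 2 on Day 22, an on-target V7 falls on Day 36, ties with the V5 sample at 7 days, and replaces it as the later one.

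**Step 5. V8.** In the immunocompromised cohorts the earliest in-window V10 falls on Day 22 + 21 = 43 of dose 2, beyond 35. No scheduled post-dose-3 sample with an in-window V8 can reach that window.

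**Step 6. Check of the remedy.** With each window closed at the dose given at that visit, an enumeration over all in-window dose days, with V7 and V10 from 7 days early to 6 days late, gives 0 misassignments.

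**The case against.** **The dosing-period layout.** The tables group visits by dosing period, with V7 under dose 2 and V10 under dose 3, so a programmer might keep a post-dose sample out of the earlier period. That would be sensible, but it is not stated. V9, V11 and V12 are counted from dose 1 although later doses have been given by then, so the layout does not end a period at the next dose.

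**Sections 6.3 and 6.4.** A reader might infer that the two sections contradict each other outright. The documents do not support that. Section 6.3's explanatory clause can be read as limiting eligibility to scheduled records, which Section 6.4 then assigns by date. Section 6.4 also confines windowing to immunogenicity, which suggests that it is the specific rule there. What stands is that the relation is unstated, including whether unscheduled, retest or early-termination results may enter a window. Excluding such results does not cure the problem, because V7 and V10 are scheduled samples. A stricter reading, in which a result counts only for its own visit number, would cure it, but Section 6.4's nearest and tie rules would then have nothing to choose between among scheduled results.

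**Doses outside the window.** A reader might extend the point to dose 2 on Days 15-21 or dose 3 on Days 125-152, where an on-target V7 or V10 would be the only candidate for the earlier visit. Those dates depart from the planned intervals, and Section 5.4 may exclude such participants under a deviation plan that is not shown. They are not relied on here.

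**Consequence.** V9 feeds no listed endpoint, and the addendum keeps only the final analysis and drops by-visit summary tables. This stands and limits the severity. The addendum still refers everything else to the main SAP, so Section 6.4 governs any visit-based immunogenicity result that is kept.

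**The mismatch.** The tables settle the Day 22 overlap by giving it to V5 and V8. Harm arises only if the text is programmed instead.

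**Conclusion.** The point holds as a minor defect in the windowing rule. As written, Section 6.4 can label a scheduled post-dose sample as the value of the visit at which that dose was given. The clearest case needs only a missing V9 result, with dose 3 and V10 both on target. Displacement of an existing sample needs an early dose, and at V5 also an early V7, except for the single on-target case that arises under the ± text. The one-day mismatch between text and tables is real and separate.

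The figures are date limits, not frequencies. How often these dates occur depends on visit tolerances that are not shown. The results rest on the visit sample being drawn before dosing on the same day, and the upward direction of error rests on the next dose raising titres. The documents do not support a claim that the primary result is materially biased.

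**What to change.** In Section 6.4:
- For V5 and immunocompetent V9, accept only samples taken before the next study dose when that dose was given.
- Assign each sample to one analysis visit only.
- Make the ±7 and ±30 text agree with the limits in Tables D and E.
- Add a sentence saying that Section 6.4 governs visit assignment for immunogenicity, and whether unscheduled, retest or early-termination results may enter a window.

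The cost is SAP wording and a small change to the windowing program. No dose, schedule or data collection changes.

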## 6.5. COMMON CALCULATIONS

Change from baseline will be calculated as:

CCI

- Change from baseline = Test value at post-baseline visit – Baseline value

If baseline is not available, the change from baseline will not be calculated and will remain missing.

## 7. STATISTICAL CONSIDERATIONS

For continuous data, descriptive statistics (i.e., n [number of subjects with available data], mean or geometric mean, standard deviation [SD], median, minimum, and maximum values) will be presented by cohort and visit, when applicable.

For categorical data, the number and percentages of subjects in each category will be presented by cohort and visit, when applicable.

### 7.1. SAMPLE SIZE CALCULATION

It is expected that approximately 360 participants will be enrolled (approximately 60 participants in each cohort). There is no statistical hypothesis testing planned for this study. Descriptive analyses will support evaluation of safety and immunogenicity.

### 7.2. MISSING DATA

Missing safety data will not be imputed. Partial or completely missing medication dates will be handled as described in [APPENDIX 1](#). Partial or completely missing medical history/concomitant illness dates will be handled similarly.

Missing immunogenicity data will be handled as described in [Section 16.1.5](#) of this analysis plan.

### 7.3. STATISTICAL TESTS

There is no formal statistical hypothesis testing planned for this study. Descriptive analyses will support evaluation of safety and immunogenicity and qualitative comparison between cohorts.

### 7.4. MULTIPLE COMPARISONS/ MULTIPLICITY

No statistical testing will be performed for this study, thus there is no need to control the overall study type I error.

CCI

## 7.5. MULTICENTER STUDIES

This study will be conducted by multiple investigators at multiple centers internationally. Data from all centers will be pooled together in the analyses and there are no plans to perform an analysis of homogeneity of the results across centers.

## 7.6. EXAMINATION OF SUBGROUPS

Subgroup analyses will be conducted as stated in Sections [16.1.1.1](#) and [16.1.3](#).

The subgroups are:

- Age group at informed consent ( $\geq 18$  to  $< 65$  years and  $\geq 65$  years)
- Sex (male and female)

## 7.7. SOFTWARE VERSION

All analyses will be conducted using SAS version 9.4 or higher.

## 8. OUTPUT PRESENTATIONS

[APPENDIX 2](#) shows conventions for presentation of data in outputs.

The templates provided with this SAP describe the presentations for this study and therefore, the format and content of the summary tables, figures, and listings to be provided by IQVIA Biostatistics.

## 9. DISPOSITION AND WITHDRAWALS

All subjects who provide informed consent will be accounted for in this study.

## 9.1. DISPOSITION

The number and percentage of participants by cohort and overall for the PAS will be presented for the below unless otherwise stated.

- Number of participants screened will be presented overall for the PAS.
- Participants with screen failure and reason for screen failure will be presented overall for the PAS.
- Participants enrolled and participants enrolled but not vaccinated.
- Participants who completed the study, ongoing in the study (primary and secondary analysis only), discontinued early from study and reasons for discontinuing early from study (percentages for reasons will be based on enrolled participants that discontinued early from the study).
- Participants vaccinated for first dose, discontinued from study before second dose and reasons for discontinuing early from study before second dose (percentages for reasons will be based on enrolled participants that discontinued from the study before second dose).
- Participants who discontinued study intervention and reasons for discontinuing study intervention (percentages for reasons will be based on enrolled participants that discontinued study intervention).
- Participants vaccinated for second dose, discontinued from study before third dose and reasons for discontinuing early from study before third dose (percentages for reasons will be based on enrolled participants that discontinued from the study before third dose).
- Participants vaccinated for third dose, discontinued from study after third dose and reasons for discontinuing early from study after third dose (percentages for reasons will be based on enrolled participants that discontinued from the study after third dose).

The number of participants included and excluded from each analysis set (including reason for exclusion) will be summarized overall and by cohort based on the PAS. A listing showing inclusion and exclusion of each subject from each analysis set, including reason for exclusion, will be provided.

The number and percentage of participants enrolled by country and site will be provided, including the dates when the first and last participants were enrolled at each site, overall and by cohort.

